5.0 STUDY POPULATION

We will recruit women with symptomatic fibroids who meet the following criteria:

INCLUSION CRITERIA

1. ≥ 21 years old
2. Premenopausal (at least one menses in last 3 months)
3. Symptomatic fibroids (fibroids visualized on ultrasound or MRI and heavy uterine bleeding, pelvic pressure or discomfort, urinary or bowel abnormalities, dyspareunia)
4. Fibroids that are ≤ 4 in total number or Fibroids that are ≤ 7 in total number if all fibroids are less than 4cm (40 mm) each.
5. Fibroids that are ≤ 7 cm (70mm) in maximum diameter, on screening imaging, if ≤ 4 fibroids in total number. (fibroid is defined as any mass with radiographic characteristics of fibroid > 2 cm or 20mm)
6. Up to date in Pap smear screening and surveillance
7. Endometrial biopsy (required if age > 45 years with irregular bleeding) does not indicate premalignant or malignant cells
8. Agree to use non-hormonal barrier method of contraception during study period if at risk for pregnancy
9. Has primary care provider or gynecologist
10. Agrees not to start new medications/treatments for fibroids during the study
11. Able to give informed consent

EXCLUSION CRITERIA

1. Fibroids treated by surgery, radiologic procedure, or GnRH agonist or antagonist in the last 3 months
2. Any submucosal fibroid ≥ 2 cm (20mm) that is $> 50\%$ in uterine cavity (FIGO Type 0 or Type 1 fibroids) amenable to hysteroscopic resection
3. Use of exogenous estrogen and/or progestin in the last month. (for 3 month long-acting depoprovera injection, no use in last 3 months)
4. Pregnant, lactating, or planning to become pregnant in the next 6 months
5. Hematocrit $< 27\%$ or visit to emergency room or hospitalization for fibroid symptoms in the last 3 months (cannot be safely randomized to a placebo)
6. History of osteopenia or osteoporosis
7. History of hyperlipidemia
8. Current liver or kidney disease
9. History of breast cancer or current breast cancer
10. Unable or unwilling to attend 4 study visits
11. Pelvic imaging concerning for gynecologic cancer or cancer of the genitourinary or gastrointestinal system
12. Does not have primary care provider or gynecologist

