6.0 MEASURED VARIABLES

6.1. Outcome Variables

Outcomes will be measured at baseline prior to randomization and at multiple time points for 6 months. Questionnaires will be administered to evaluate patient-reported fibroid symptoms, study medication compliance, adverse events, and the rate of recurrence for fibroid symptoms. In the following section, outcome measurements are described in detail.

6.1.A Questionnaires to Assess Symptoms

These are validated questionnaires to assess the change in symptoms over time.

1. Uterine Fibroid Symptom-Quality of Life (UFS-QOL): The Uterine Fibroid Symptom and Quality of Life Questionnaire (UFS-QOL) will be the primary outcome to assess fibroid symptoms. The UFS-QOL is a validated fibroid-specific questionnaire that assesses fibroid symptoms and their impact on quality-of-life.^{20,21}
2. EuroQoL 5-D: The EuroQoL 5D is a widely used, validated questionnaire to assess overall quality of quality of life across a broad spectrum of diseases.
3. Menstrual Impact Questionnaire (MIQ): The MIQ is a 12-question, validated questionnaire to determine the impact of heavy menstrual bleeding on a woman's quality of life.²⁴ The MIQ has been used in trials of heavy bleeding that includes women with uterine fibroids.

6.1.B Pelvic Ultrasound

Pelvic ultrasound including trans-abdominal and trans-vaginal images will be used to assess changes in uterine volume as well as fibroid number, size, and volume from baseline to the end of month 2, 4 and 6. All pelvic ultrasound will be performed by either [name] or [name], faculty members in the Division of Reproductive Endocrinology and Infertility (REI) in the Department of Obstetrics, Gynecology, and Reproductive Sciences. [name] and [name] have specialty training in performing pelvic ultrasound to assess uterine fibroids as well as ovarian cysts. They perform up to 100 pelvic ultrasounds every week in their clinical practice and their expertise in this area will be invaluable. All pelvic ultrasound will be performed in a private room within the Ob/Gyn Division of Reproductive Medicine clinical space located adjacent to Mission Bay Hospital at [name] or Mt Zion Women's Health.

6.1.C Serum hormone levels

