Estradiol and follicle-stimulating hormone (FSH) levels will be measured at baseline and the end of month 2, 4 and 6. These hormones will detect the development of hypoestrogenism and assess changes in the hypothalamic-pituitary-ovarian axis that regulate normal menstrual function. All blood draws will be performed by certified phlebotomists in the REI practice.

6.1.D Total Cholesterol

Since hyperlipidemia is a rare side effect of letrozole, total cholesterol will be measured at baseline and month 6. All blood draws will be performed by certified phlebotomists in the REI practice. Approximately 5 ml (1 tsp) will be drawn at Baseline and Month 6 for this test.

6.1.E Other Outcomes

Other outcomes related to study intervention and fibroid symptoms will include measures related to:

Treatment Failure: We will ask participants to report any additional fibroid treatments including medical management for fibroid-related symptoms, myomectomy, hysterectomy, uterine artery embolization, MR Guided Focused Ultrasound, endometrial ablation, dilation and curettage, or any new and emerging fibroid treatments.

Adverse Events

This is the first trial of letrozole monotherapy for >12 weeks among premenopausal women. Therefore, a full range of adverse events will be assessed every 2 months for all body systems including known potential side effects such as hot flashes, myalgias, and fatigue as well as unknown side effects that will be identified by using the open ended question "Have you had any changes to your health that impact your ability to perform your normal activities?". In addition to assessing adverse events monthly during the trial, we will query participants about adverse events 30 days after completing the last dose of medication.

Pregnancy and pregnancy outcomes: In this study pregnancy is considered a Serious Adverse Event. Participants will report all known pregnancies while receiving study medication. For each pregnancy, we will query participants about whether the pregnancy resulted in a miscarriage, abortion, or continued pregnancy. For continued pregnancies, we will ask participants to report obstetric outcomes including gestational age at birth, mode of delivery (vaginal or cesarean), and complications (e.g. placenta previa, placental abruption, preeclampsia).

6.1.F Long-term storage of blood

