During blood draws at baseline and month 2, 4, and 6, we will ask participants if they are willing to allow long-term storage of their blood (serum) for future fibroid studies. Participants may decline this long term storage and still participate in the study. Specimens will be stored long-term in the Specimen Bank within the UCSF Reproductive Medicine Lab.

6.1.G Schedule of Outcomes Assessment

Outcomes will be assessed at varying timepoints from Baseline to 6 months (Table 2). In-person study visits will occur prior to randomization at the Baseline Visit (BV), Month 2, Month 4, and Month 6. All other visit data will be collected through mailed or on-line questionnaires, and/or phone interviews.

	BV	Mo 1	2	3	4	5	6	7
Symptom questionnaires	X	X	X	X	X	X	X	
EQ5D questionnaire	X		X		X		X	
Pelvic ultrasound	X		X		X		X	
Hormone levels	X		X		X		X	
Total Cholesterol	X						X	
Adverse event assessment		X	X	X	X	X	X	X
Specimen Storage*	X		X		X		X	
Compensation	\$25		\$25		\$25		\$25	

*Optional

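### Low hematocrit is a stated reason against placebo at entry, but no hematocrit is scheduled afterwards, and Group B starts a second placebo block at month 5 without a recheck

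*Combined protocol and SAP*

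**What the plan says.** Section 5.0, exclusion criterion 5, sets a hematocrit limit of 27% and joins it to a second condition: "visit to emergency room or hospitalization for fibroid symptoms in the last 3 months (cannot be safely randomized to a placebo". The parenthesis gives the reason for the criterion. Hematocrit is mentioned nowhere else in the combined protocol and SAP.

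Section 3.0 gives Group B two months of placebo, two of letrozole, and two more of placebo. Group A takes letrozole throughout.

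The scheduled blood tests are hormones and cholesterol. Section 6.1.C: "Estradiol and follicle-stimulating hormone (FSH) levels will be measured at baseline and the end of month 2, 4 and 6". Section 6.1.D adds total cholesterol at baseline and month 6. Section 6.1.F confirms the draws when it describes optional storage: "During blood draws at baseline and month 2, 4, and 6". They match the visits in section 6.1.G: "In-person study visits will occur prior to randomization at the Baseline Visit (BV), Month 2, Month 4, and Month 6".

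Other provisions bear on the same risk:

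- Inclusion criterion 9 (section 5.0): "Has primary care provider or gynecologist".
- Inclusion criterion 10 (section 5.0): "Agrees not to start new medications/treatments for fibroids during the study".
- Section 6.1.A includes a "validated questionnaire to determine the impact of heavy menstrual bleeding", and Table 2 lists the symptom questionnaires every month.
- Section 6.1.E assesses adverse events "for all body systems including known potential side effects such as hot flashes, myalgias, and fatigue", and Table 2 lists this assessment monthly through month 7.
- Section 8.0 sends serious events to the safety monitor within 24 hours and adverse event updates every 3 months. It sets no stopping rule.

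**The concern.** The protocol judges that below a certain hematocrit a woman should not be assigned to placebo. That judgement is applied once, at entry. Group B then goes onto placebo twice, and by the second time four months have passed since randomization, two of them on placebo. Heavy bleeding is one of the qualifying symptoms, so hematocrit can plausibly move in this population.

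Women also agree not to start other fibroid treatments while enrolled, and there is no stopping rule. Whether a woman should go on is therefore left to clinical judgement, and the investigator has no scheduled value of the quantity that the protocol itself links to placebo safety. At stake is participant safety in a small group. No estimate or test is affected.

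**Working it through.** There is no figure in the plan to reproduce. The check sets the criterion beside the schedule and then counts the cost of closing the gap.

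**1. Where hematocrit could appear.** Sections 6.1.A to 6.1.G list questionnaires, ultrasound, estradiol and FSH, total cholesterol, treatment failure, adverse events, pregnancy and stored serum. Table 2 repeats the scheduled items. The objective baseline measures in section 6.2.A are weight, height, vital signs, and uterine, fibroid and ovarian findings. Sections 7.0 and 8.0 name no laboratory test. Scheduled hematocrits after entry: 0. Scheduled blood draws after entry: 3 per woman (months 2, 4 and 6).

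**2. Group B's placebo exposure against the existing draws.** Placebo months: 2 + 2 = 4 of 6.

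| Draw (end of month) | Position in Group B | What a hematocrit could inform |
|---|---|---|
| 2 | End of first placebo block | Whether the value fell on placebo; whether to continue |
| 4 | End of letrozole, just before second placebo block | Whether the entry condition still holds as placebo resumes |
| 6 | End of second placebo block, dosing over | Referral only |

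Month 4 matters most. It falls where the entry question arises again.

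**3. What the existing surveillance would detect.** The questionnaires record symptoms and the impact of bleeding. The adverse event assessment covers all body systems and names fatigue, but its open question asks about health changes that affect normal activities. The required primary care provider or gynecologist may order a blood count, but the protocol neither asks for one nor routes the result to the investigator. A gradual fall that the woman tolerates could pass through all of these.

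**4. Assays needed.** Inputs: 20 women (section 3.0) and the draws above.

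- Months 2 and 4: 20 × 2 = 40.
- Months 2, 4 and 6: 20 × 3 = 60.
- If the 10% short-term attrition in section 10.0 applied to every follow-up visit (an assumption): 18 × 2 = 36, or 18 × 3 = 54.

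New visits: 0. New venipunctures: 0.

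**5. Size of the risk.** The documents do not say how many women will have heavy bleeding, enter near 27%, or fall below it. No event rate can be derived.

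**The case against.** The strongest reply is that an entry threshold does not by itself oblige the trial to measure the same variable serially. Symptoms and adverse events are asked about monthly, serious events reach the monitor within a day, every woman has an outside clinician, and placebo never runs longer than two months at a stretch. Section 6.1.E also records additional fibroid treatments under treatment failure, so rescue is foreseen. All of this stands, and it is why the point is an improvement and not an error. It does not supply a hematocrit value when Group B returns to placebo.

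A second reply concerns the remedy: no existing draw falls inside a placebo block, and a month 6 value comes too late to affect dosing. This also stands. Month 6 is therefore optional, and the limit is stated with the fix.

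A reader might infer something stronger: that because Table 2 lists no hematocrit, exclusion 5 goes unmeasured and women may be randomized without a value. The documents do not support that. Table 2 is a schedule of outcomes and omits other eligibility checks too, such as pregnancy and endometrial biopsy. Inclusion criterion 5 refers to screening imaging, so screening steps exist outside the table. A numeric exclusion cannot be applied without a number, and clinic records or the planned manual of operations (section 2.0) may supply it. What is left at entry is a missing detail: the source of the value and how old it may be. The three-month window reads most naturally with the emergency visit or hospitalization, so it may not cover hematocrit.

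**Conclusion.** The concern holds for follow-up. The protocol gives placebo safety as the reason for a criterion that includes low hematocrit, schedules no hematocrit after entry, and starts a second two-month placebo block for Group B at month 5 without a recheck. Up to 10 women are affected, given 20 randomized 1:1. The remaining gap is narrow: a fall that symptoms, adverse event questions and outside care do not reveal.

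At entry only a minor clarification is needed. A reader might also infer that the trial is unsafe as designed, or that 27% ought to be a stopping threshold. The documents give no anemia rate and no basis for either conclusion. The point rests on the text of the criterion and the schedule, and on the assumption that the manual of operations and the monitoring charter, which were not available, do not already require follow-up blood counts. The primary outcome, power and analysis are unaffected.

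**What to change.** 1. Add a hematocrit (one whole-blood tube) to the existing month 2 and month 4 draws in both groups. Testing both groups protects the blind. Month 6 is optional and serves referral only.
2. Send any value below 27% promptly to the investigator for clinical judgement. Review month 4 results as soon as they are available, around the start of the second placebo block. State that 27% is a notification level borrowed from the entry criterion and not a stopping rule.
3. Include the values in the safety monitor's regular updates.
4. Minor clarification: state the source and maximum age of the entry hematocrit, for example a documented recent value, or a value from the baseline draw reviewed before randomization. The second option may mean a short wait for the result.

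Cost: 40 assays, or 60 with month 6, if all 20 women complete; one extra tube per draw; one row in Table 2; and a small protocol and consent update. The follow-up tests need no new visit, venipuncture or staff. Any assays at baseline would be additional, and accepting a documented value keeps them few. Limit: a fall within a placebo block is still found only at its end.

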5.1 Participant Recruitment

We will identify potentially eligible participants with symptomatic fibroids who present to the UCSF Women's Health Center and the UCSF Comprehensive Fibroid Center (CFC) where [name] sees patients. The CFC is a high volume specialty clinic that offers the full range of available surgical and nonsurgical treatments. Many women come to the CFC seeking minimally invasive interventions because of our ongoing trials of new and emerging fibroid treatments as described in Preliminary Data. There are 20-25 new fibroid consultations per week among the CFC physicians; many of these patients inquire about the availability of medical management of

their symptoms. The patient population is racially and ethnically diverse with a general enthusiasm for supporting fibroid studies. Therefore, we believe it is feasible to recruit 20 women to this pilot trial over 6 months in this pilot study.

Participants will also be recruited from the greater San Francisco Bay Area community. The investigative team will use a multi-component IRB-approved recruitment approach, including contacting a database of women with fibroids who have given permission to be contacted about future research opportunities, direct community-based media efforts (newspaper notices, radio advertising, brochures in local clinics, talks to local community groups, notices in churches), social media/networking sites). Recruitment efforts will be based at UCSF. To facilitate recruitment.

5.2 Informed Consent

Before entering the study, all study procedures, time requirements, risks and potential benefits will be explained to each potential study participant using the information in the UCSF IRB-approved informed consent form. The potential study participant will be given adequate time to read the informed consent document and ask questions. Eligible participants who choose to enter the study will sign the informed consent form and Health Insurance Portability and Accountability Act (HIPAA) form prior to beginning the study intervention. Each participant will be given a copy of the signed documents and the original will be a part of the research record. All study-specific data will be kept confidential and stored in locked files at the clinical center.

6.0 MEASURED VARIABLES

6.1. Outcome Variables

Outcomes will be measured at baseline prior to randomization and at multiple time points for 6 months. Questionnaires will be administered to evaluate patient-reported fibroid symptoms, study medication compliance, adverse events, and the rate of recurrence for fibroid symptoms. In the following section, outcome measurements are described in detail.

6.1.A Questionnaires to Assess Symptoms

These are validated questionnaires to assess the change in symptoms over time.

1. Uterine Fibroid Symptom-Quality of Life (UFS-QOL): The Uterine Fibroid Symptom and Quality of Life Questionnaire (UFS-QOL) will be the primary outcome to assess fibroid symptoms. The UFS-QOL is a validated fibroid-specific questionnaire that assesses fibroid symptoms and their impact on quality-of-life.^{20,21}
2. EuroQoL 5-D: The EuroQoL 5D is a widely used, validated questionnaire to assess overall quality of quality of life across a broad spectrum of diseases.
3. Menstrual Impact Questionnaire (MIQ): The MIQ is a 12-question, validated questionnaire to determine the impact of heavy menstrual bleeding on a woman's quality of life.²⁴ The MIQ has been used in trials of heavy bleeding that includes women with uterine fibroids.

6.1.B Pelvic Ultrasound

Pelvic ultrasound including trans-abdominal and trans-vaginal images will be used to assess changes in uterine volume as well as fibroid number, size, and volume from baseline to the end of month 2, 4 and 6. All pelvic ultrasound will be performed by either [name] or [name], faculty members in the Division of Reproductive Endocrinology and Infertility (REI) in the Department of Obstetrics, Gynecology, and Reproductive Sciences. [name] and [name] have specialty training in performing pelvic ultrasound to assess uterine fibroids as well as ovarian cysts. They perform up to 100 pelvic ultrasounds every week in their clinical practice and their expertise in this area will be invaluable. All pelvic ultrasound will be performed in a private room within the Ob/Gyn Division of Reproductive Medicine clinical space located adjacent to Mission Bay Hospital at [name] or Mt Zion Women's Health.

6.1.C Serum hormone levels

Estradiol and follicle-stimulating hormone (FSH) levels will be measured at baseline and the end of month 2, 4 and 6. These hormones will detect the development of hypoestrogenism and assess changes in the hypothalamic-pituitary-ovarian axis that regulate normal menstrual function. All blood draws will be performed by certified phlebotomists in the REI practice.

6.1.D Total Cholesterol

Since hyperlipidemia is a rare side effect of letrozole, total cholesterol will be measured at baseline and month 6. All blood draws will be performed by certified phlebotomists in the REI practice. Approximately 5 ml (1 tsp) will be drawn at Baseline and Month 6 for this test.

6.1.E Other Outcomes

Other outcomes related to study intervention and fibroid symptoms will include measures related to:

Treatment Failure: We will ask participants to report any additional fibroid treatments including medical management for fibroid-related symptoms, myomectomy, hysterectomy, uterine artery embolization, MR Guided Focused Ultrasound, endometrial ablation, dilation and curettage, or any new and emerging fibroid treatments.

Adverse Events

This is the first trial of letrozole monotherapy for >12 weeks among premenopausal women. Therefore, a full range of adverse events will be assessed every 2 months for all body systems including known potential side effects such as hot flashes, myalgias, and fatigue as well as unknown side effects that will be identified by using the open ended question "Have you had any changes to your health that impact your ability to perform your normal activities?". In addition to assessing adverse events monthly during the trial, we will query participants about adverse events 30 days after completing the last dose of medication.

Pregnancy and pregnancy outcomes: In this study pregnancy is considered a Serious Adverse Event. Participants will report all known pregnancies while receiving study medication. For each pregnancy, we will query participants about whether the pregnancy resulted in a miscarriage, abortion, or continued pregnancy. For continued pregnancies, we will ask participants to report obstetric outcomes including gestational age at birth, mode of delivery (vaginal or cesarean), and complications (e.g. placenta previa, placental abruption, preeclampsia).

6.1.F Long-term storage of blood

During blood draws at baseline and month 2, 4, and 6, we will ask participants if they are willing to allow long-term storage of their blood (serum) for future fibroid studies. Participants may decline this long term storage and still participate in the study. Specimens will be stored long-term in the Specimen Bank within the UCSF Reproductive Medicine Lab.

6.1.G Schedule of Outcomes Assessment

Outcomes will be assessed at varying timepoints from Baseline to 6 months (Table 2). In-person study visits will occur prior to randomization at the Baseline Visit (BV), Month 2, Month 4, and Month 6. All other visit data will be collected through mailed or on-line questionnaires, and/or phone interviews.

	BV	Mo 1	2	3	4	5	6	7
Symptom questionnaires	X	X	X	X	X	X	X	
EQ5D questionnaire	X		X		X		X	
Pelvic ultrasound	X		X		X		X	
Hormone levels	X		X		X		X	
Total Cholesterol	X						X	
Adverse event assessment		X	X	X	X	X	X	X
Specimen Storage*	X		X		X		X	
Compensation	\$25		\$25		\$25		\$25	

*Optional

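### No on-treatment pregnancy test or drug-hold rule is named, so an unrecognised early pregnancy could start letrozole (Group B, month 2) or continue on it (Group A, months 2 and 4)

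*Combined protocol and SAP*

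**What the plan says.** **Entry.** Section 5.0 excludes women who are "Pregnant, lactating, or planning to become pregnant in the next 6 months" and requires participants to "Agree to use non-hormonal barrier method of contraception during study period if at risk for pregnancy". It names no test by which pregnancy is ruled out.

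**On treatment.** Section 6.1.E states: "In this study pregnancy is considered a Serious Adverse Event". Detection is by report: "Participants will report all known pregnancies while receiving study medication". The rest of that paragraph is about collecting the outcome of each pregnancy.

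**Blood tests.** Section 6.1.C: "Estradiol and follicle-stimulating hormone (FSH) levels will be measured at baseline and the end of month 2, 4 and 6". The stated purpose is to detect hypoestrogenism and follow the ovarian axis. Neither that section nor Table 2 in Section 6.1.G lists hCG.

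**Contacts.** Section 6.1.E says that "a full range of adverse events will be assessed every 2 months for all body systems", and adds a monthly assessment: "In addition to assessing adverse events monthly during the trial". Table 2 shows adverse-event contacts at months 1 to 7. In-person visits are at baseline and months 2, 4 and 6; for the other months, "All other visit data will be collected through mailed or on-line questionnaires, and/or phone interviews".

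**Action.** Sections 7.2 and 8.0 deal with reporting, including a 24-hour report of serious events to the safety monitor. They give no instruction on study drug for a woman found to be pregnant.

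**The concern.** The protocol treats pregnancy on study drug as something to prevent, yet its stated detection method works only after the woman knows. Recognition may be slow in this population. Eligibility requires only one menses in three months, and irregular bleeding is foreseen in the biopsy criterion. The open-ended adverse-event question asks about health changes that interfere with normal activities, which an early pregnancy need not do. The required contraception is a barrier method, and recent hormonal use is excluded. Section 1.0 also notes that letrozole is used to induce ovulation. That is in other populations, but it is a reason not to assume that conception on treatment cannot happen.

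The end of month 2 matters most. Group B then moves from placebo to its first letrozole, at a visit where blood is already being drawn. A pregnancy identified there would avoid exposure altogether. What is at stake is participant safety, not the trial's inference.

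**Working it through.** The plan gives no figure on this point to reproduce. The check has two parts: what could detect a pregnancy at each visit, and how much letrozole follows a missed one.

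**Step 1. What each planned procedure can detect**
- Self-report (6.1.E): pregnancies the woman already knows about.
- Ultrasound at months 2, 4 and 6 (6.1.B): a pregnancy advanced enough to be seen. The stated purpose is uterine and fibroid measurement, but a visible pregnancy would probably be noticed.
- Menstrual questionnaire (6.1.A, within the monthly symptom questionnaires of Table 2): may prompt a woman to notice a missed period; it is not a pregnancy test.
- Adverse-event contacts, months 1 to 7: an opportunity to report. The text does not say that they ask about pregnancy specifically.
- Estradiol and FSH (6.1.C): not assigned to excluding pregnancy.

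What remains is a pregnancy that, at the visit, is too early for the scan and not yet recognised.

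**Step 2. What drug follows each visit**

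Inputs: 20 women randomised 1:1, so 10 per group; the dosing schedule in Section 3.0; no dropout; all women counted as at risk.

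| Visit (end of) | Group A next | Group B next | Letrozole blocks begun |
|---|---|---|---|
| Month 2 | Letrozole (continues) | Letrozole (first exposure) | 10 + 10 = 20 |
| Month 4 | Letrozole (continues) | Placebo | 10 + 0 = 10 |
| Month 6 | None | None | 0 |

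Total: 20 + 10 + 0 = 30 two-month blocks, of which 10 are first exposures.

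**Step 3. Length of exposure if a pregnancy is missed at one of these visits**
- Reported at the next monthly contact: about 1 month × 30 daily doses = about 30 doses.
- Found only at the next scan: about 2 months × 30 = about 60 doses.

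**Step 4. Tests needed**
- Months 2 and 4, all women: 20 × 2 = 40. Of these, 30 precede letrozole; the other 10 (Group B at month 4) are there to keep the blind.
- With baseline: 20 × 3 = 60.
- A month-6 test follows the last dose and prevents no exposure.

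No probability is calculated. The documents give neither the number of women at risk of pregnancy nor a conception rate.

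**The case against.** The strongest reply is that silence here is weak evidence. Table 2 is a schedule of outcomes, not of all procedures: hematocrit, Pap status and endometrial biopsy are eligibility requirements with no row in it. The manual of operations and the DSMB charter are mentioned but not supplied, the consent pages were removed, and the protocol gives no dispensing schedule, where a test-before-supply rule might sit. This stands. A reader might infer that women were enrolled or treated without any pregnancy test. The documents do not support that; they show only that the supplied text names none.

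The second reply is that several safeguards overlap: barrier contraception for women at risk, exclusion of women planning pregnancy, a monthly menstrual questionnaire, monthly adverse-event contacts that would naturally collect a listed serious event, and a scan at the Group B switch by faculty who perform as many as 100 a week. This also largely stands, and narrows the gap to a contraception failure shortly before a visit. It does not close it, because none of these measures finds a pregnancy that is both unrecognised and too early to see.

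Third, the documents contain no statement of fetal risk from letrozole, so a reader who infers a harm of known size goes beyond them. The point needs only the protocol's own position that pregnancy is an exclusion and a Serious Adverse Event.

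Finally, Section 8.0 declines a stopping rule. A reader might take that to mean that drug continues after a known pregnancy. It does not say so: the statement concerns the trial as a whole, and the text is simply silent on the individual participant.

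**Conclusion.** The point holds in a limited form and is minor. As written, the protocol relies on self-report with incidental help, and it states no participant-level hold or stop rule. An early pregnancy neither recognised nor visible at month 2 could begin letrozole in Group B or continue on it in Group A; at month 4 only Group A is affected.

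The 30 blocks and the 30 to 60 doses are ceilings. They assume full retention and every woman at risk, and the upper dose figure also assumes that a pregnancy passes unrecognised through a monthly contact. They should not be read as expected exposure or turned into a probability. That the event is likely rare is a judgement from the safeguards in place; the documents give no rate. Sample size, the UFS-QOL analysis and the trial's conclusions are unaffected. If a test and a hold rule exist in documents not supplied, what remains is to state them in the protocol.

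**What to change.** 1. Test all women in both groups, which keeps the blind, with urine hCG at the visit or serum hCG on blood already drawn. Do this at baseline (or state the existing test) and at months 2 and 4, with the result known before the next supply is taken. Add the row to Table 2.
2. State that study drug is held on a positive test and stopped if pregnancy is confirmed, and that the pregnancy is reported as a Serious Adverse Event.
3. Ask about pregnancy specifically at the monthly contacts and at month 7. A visit test cannot find a conception that occurs soon afterwards; this question gives such cases an earlier chance of being found.
4. Treat a month-6 test as optional, for ascertainment only.

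The cost is at most 40 on-treatment tests (60 with baseline), one table row, one sentence on drug, one question at existing contacts and a short amendment. Serum testing adds a short wait before the next supply, so the release of drug would need to be settled; urine testing at the visit avoids this. Sample size and analysis do not change. Because the pilot's forms and manual are meant to carry over to the multi-site trial, the change would carry over too.
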